4.2. Scientific rationale for study design

The study will evaluate the safety and immunogenicity of H7N9 antigen (A/Hong Kong/125/2017) in combination with full or half doses of AS03 adjuvant system.

Non-adjuvanted H7 influenza antigens have been poorly immunogenic in vaccine studies to date. For this reason, GSK anticipates that an adjuvanted vaccine, administered as a two-dose series, will be required to elicit a potentially protective immune response.

The inclusion of a placebo control group in this observer-blind study will permit unbiased assessment of vaccine safety and reactogenicity.

4.3. Justification for dose

The rationale for evaluating 1.9 µg, 3.75 µg and 7.5 µg doses of H7N9 antigen is based on the Biomedical Advanced Research and Development Authority (BARDA) requirement to assess the dose-sparing ability of influenza A/Hong Kong/125/2017-like (H7N9) virus vaccine in combination with full or half doses of AS03. All 3 antigen doses have been part of GSK's clinical development program with an AS03-adjuvanted split virus H5N1 and H7N9 influenza vaccines.

AS03_A (11.86 mg tocopherol in 0.25 mL) and AS03_B (5.93 mg tocopherol in 0.125 mL) will be evaluated in this study, since both AS03 formulations have been shown to improve the immunogenicity of inactivated split-virion H5N1 and H7N9 influenza vaccines in studies conducted by GSK.

4.4. End of Study definition

A participant is considered to have completed the study if he/she is available for the last scheduled contact at Month 13 as described in the protocol.

End of Study: Last subject last visit (telephone contact at Month 13).

5. STUDY POPULATION

5.1. Inclusion criteria for enrollment

Adherence to these criteria as specified in the protocol is essential. Inclusion criteria deviations are not allowed because they can jeopardize the scientific integrity or regulatory acceptability of the study or participant safety.

All participants must satisfy ALL of the following criteria at study entry:

1. Healthy participants as established by medical history and clinical examination before entering into the study.
2. A male or female ≥ 18 years of age at the time of first vaccination.
3. Participants, who, in the opinion of the investigator, can and will comply with the requirements of the protocol (e.g. completion of the diary cards and COVID-19 assessment card, return for follow-up visits, or return the diary cards and COVID-19 assessment card in a timely manner using the pre-stamped envelope received at the site).
4. Written or witnessed/thumb printed informed consent obtained from the participant prior to performance of any study specific procedure.
5. Female participants of non-childbearing potential may be enrolled in the study. Non-childbearing potential is defined as pre-menarche, current bilateral tubal ligation or occlusion hysterectomy, bilateral ovariectomy or post-menopause.

Female participants of childbearing potential may be enrolled in the study, if the participant:

- has practiced adequate contraception for 1 month prior to vaccination, and
- has a negative pregnancy test on the day of vaccination, and
- has agreed to continue adequate contraception during the entire treatment period and for 2 months after completion of the vaccination series.

Refer to Section 10.5.1 for definitions of women of childbearing potential and adequate contraception.

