● is used to indicate a study procedure that requires documentation in the individual eCRF.

○ is used to indicate a study procedure that does not require documentation in the individual eCRF.

¹ Medical history data should include the presence or absence or risk factors for complications associated with influenza. Influenza vaccination history covers influenza vaccines administered in the previous 3 influenza seasons (if any).

² At a minimum, temperature and vital signs (e.g. heart rate and respiratory rate, blood pressure) must be collected prior to vaccination. Clinically significant abnormalities are to be captured in the eCRF as adverse events.

³ Urine pregnancy test to be performed for women of childbearing potential; a negative result must be obtained prior to each vaccination.

⁴ Fever is defined as temperature $\geq 38.0^{\circ}\text{C}/100.4^{\circ}\text{F}$. The preferred location for measuring temperature in this study will be oral. Participants with a minor illness (such as mild diarrhea, mild upper respiratory infection) without fever may be enrolled and/or vaccinated at the discretion of the investigator.

⁵ Diary cards used to capture both solicited administration site and systemic events (Days 1-7 after each vaccination) and unsolicited adverse events (Days 1-21 after each vaccination) and COVID-19 assessment cards are provided at the time of each vaccination and collected at the next visit following each vaccination (solicited administration and systemic events portion of card) and at the subsequent visit (unsolicited adverse events portion of card) or by mail using the pre-stamped envelope received at the site.

⁶ Participant records occurrence, intensity, and duration of solicited administration site events and of each solicited systemic event and unsolicited adverse event. Investigator or delegate later assesses and records relationship of each unsolicited adverse event.

eCRF: electronic case report form; MAEs: medically attended adverse events; Pre-Vacc: pre-vaccination; pIMDs: potential immune-mediated diseases; Post-Vacc: post-vaccination; SAEs: serious adverse events; TC: telephone contact

Table 2 Intervals between study visits

Interval (by visit number)	Interval (by visit name)	Optimal interval length ¹ (Days)	Allowed interval (Study Day)
Visit 1 - TC1	Visit Day 1 - Telephone Contact Day 8	7	6-10
Visit 1 - Visit 2	Visit Day 1 - Visit Day 22	21	18-25 ²
Visit 2 - TC2	Visit Day 22 - Telephone Contact Day 29	7	26-30

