10.4.1. COVID-19 assessment card

CCI - This section contained Clinical Outcome Assessment data collection questionnaires or indices, which are protected by third party copyright laws and therefore have been excluded.

CONFIDENTIAL

[figure not shown]
209671 (FLU Q-PAN H7N9=AS03-002)

CCI - This section contained Clinical Outcome Assessment data collection questionnaires or indices, which are protected by third party copyright laws and therefore have been excluded.

Final

CCI - This section contained Clinical Outcome Assessment data collection questionnaires or indices, which are protected by third party copyright laws and therefore have been excluded.

A large black rectangular box covers the majority of the page content, starting below the red text and extending down to the bottom of the page, effectively redacting the excluded clinical outcome assessment data.

10.5. Appendix 5: Contraceptive guidance and collection of pregnancy information**10.5.1. Definitions****10.5.1.1. Women of childbearing potential**

A woman is considered fertile following menarche and until becoming postmenopausal unless permanently sterile (see below).

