10.5.1.1.1. Women not considered as women of childbearing potential

- Premenarchal

Menarche is the onset of menses for the first time in a young female and is preceded by several changes associated with puberty including breast development and pubic hair growth.

If fertility is unclear (e.g. amenorrhea in adolescents or athletes) and a menstrual cycle cannot be confirmed before first dose of study intervention, additional evaluation should be considered.

- Premenopausal female with ONE of the following:
 - Documented hysterectomy
 - Documented bilateral salpingectomy
 - Documented bilateral oophorectomy

Note: Documentation can come from the site personnel's: review of participant's medical records, medical examination, or medical history interview.

- Postmenopausal female

A postmenopausal state is defined as no menses for 12 months without an alternative medical cause. A high follicle stimulating hormone level in the postmenopausal range may be used to confirm a postmenopausal state in women not using hormonal contraception or hormonal replacement therapy (HRT). However, in the absence of 12 months of amenorrhea, a single follicle stimulating hormone measurement is insufficient.

- Females on HRT and whose menopausal status is in doubt will be required to use 1 of the non-hormonal highly effective contraception methods if they wish to continue their HRT during the study. Otherwise, they must discontinue HRT to allow confirmation of postmenopausal status before study enrollment.

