10.5.2. Contraception guidance

- Female participants of childbearing potential are eligible to participate if they agree to use an adequate contraception consistently and correctly according to the methods listed in GSK list of highly effective contraceptive methods provided in [Table 21](#).

Table 21 Highly effective contraceptive methods

Highly Effective Contraceptive Methods That Are User Dependent ^a Failure rate of <1% per year when used consistently and correctly.	
Combined (estrogen- and progestogen-containing) hormonal contraception associated with inhibition of ovulation	

 Oral Intravaginal Transdermal 	
Progestogen-only hormonal contraception associated with inhibition of ovulation	

 injectable 	
Highly Effective Methods That Are User Independent	

 Implantable progestogen-only hormonal contraception associated with inhibition of ovulation Intrauterine device Intrauterine hormone-releasing system Bilateral tubal occlusion 	
Vasectomized partner	

(A vasectomized partner is a highly effective contraception method provided that the partner is the sole male sexual partner of the woman of childbearing potential and the absence of sperm has been confirmed. If not, an additional highly effective method of contraception should be used.)
	
Male partner sterilization prior to the female participant's entry into the study, and this male is the sole partner for that participant,	

(The information on the male sterility can come from the site personnel's review of the participant's medical records; medical examination and/or semen analysis, or medical history interview provided by her or her partner.)
	
Sexual abstinence	

(Sexual abstinence is considered a highly effective method only if defined as refraining from heterosexual intercourse during the entire period of risk associated with the study intervention. The reliability of sexual abstinence needs to be evaluated in relation to the duration of the study and the preferred and usual lifestyle of the participant.)
	

NOTES:

^a Typical use failure rates may differ from those when used consistently and correctly. Use should be consistent with local regulations regarding the use of contraceptive methods for participants in clinical studies.

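### Inclusion criterion 5 and Section 10.5.1.1.1 classify women with tubal ligation or occlusion differently, leaving it unclear whether their pre-dose pregnancy test is mandatory (minor)

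*Protocol*

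**What the plan says.** Criterion 5 in Protocol Section 5.1 carries its own definition: "Non-childbearing potential is defined as pre-menarche, current bilateral tubal ligation or occlusion hysterectomy, bilateral ovariectomy or post-menopause". A comma is evidently missing after the word occlusion, since an occlusion hysterectomy is not a procedure. Read sensibly, the criterion places women with a current bilateral tubal ligation or occlusion outside childbearing potential.

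The criterion then sets three conditions for women of childbearing potential only. One is that the participant "has a negative pregnancy test on the day of vaccination". It closes with a cross-reference: "Refer to Section 10.5.1 for definitions of women of childbearing potential and adequate contraception".

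Section 10.5.1.1 treats a woman as fertile from menarche to menopause unless she is permanently sterile, and refers to the list that follows. That list, in Section 10.5.1.1.1, has an entry headed "Premenopausal female with ONE of the following", with three documented procedures under it: hysterectomy, bilateral salpingectomy and bilateral oophorectomy.

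Section 10.5.2 introduces Table 21 with the words "Female participants of childbearing potential are eligible to participate if they agree to use an adequate contraception consistently and correctly". Among the user-independent methods, Table 21 lists "Bilateral tubal occlusion".

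The testing rule in the Schedule of Activities (Section 1.3, footnote 3) reads: "Urine pregnancy test to be performed for women of childbearing potential; a negative result must be obtained prior to each vaccination". Protocol Section 8.2.1.7 and SAP Section 9.5 restrict the test to the same women.

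**The concern.** The protocol puts the same woman in two classes. A premenopausal participant with a tubal ligation or occlusion is not of childbearing potential by the definition inside criterion 5, but is of childbearing potential by the section that criterion 5 cites. Nothing says which text governs.

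The class matters because it decides whether a negative urine test is required before each dose. The exclusion of pregnant women (Section 5.2.4) and the bar on further doses after a pregnancy (Section 10.3.7.1) apply to everyone. Where no test is done, however, they rest on what the woman knows and reports. At stake is the uniform application of one pre-vaccination safety check across sites, not any analysis.

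**Working it through.** The plan gives no figure to reproduce, so the check is a comparison of texts.

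**Step 1. How each text classes a premenopausal woman.**

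| Procedure | Criterion 5 | Section 10.5.1.1.1 | Table 21 |
|---|---|---|---|
| Bilateral tubal ligation | not of childbearing potential | not listed, so of childbearing potential | not named |
| Bilateral tubal occlusion | not of childbearing potential | not listed, so of childbearing potential | listed as contraception |
| Hysterectomy | not of childbearing potential | same, if documented | not listed |
| Bilateral removal of the ovaries | not of childbearing potential | same, if documented | not listed |
| Bilateral salpingectomy | not listed | not of childbearing potential, if documented | not listed |

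The lists differ in both directions: criterion 5 adds ligation and occlusion, and omits salpingectomy. Dropping the word occlusion would not remove the conflict, because ligation would still be in one list and not the other.

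**Step 2. What follows for testing.** Under the inline definition, no test is required at Visit 1 or Visit 2 for women with ligation or occlusion, though none is forbidden. Under Section 10.5.1, a negative result is required at both visits.

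**Step 3. Where the cross-reference leads.** It promises definitions of childbearing potential and of adequate contraception in Section 10.5.1. Only the first is there; the contraceptive methods are in Section 10.5.2.

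**Step 4. Bounds on the number.** Section 4.1 plans 60 participants aged 18 to 64 in each of 7 groups, so 7 × 60 = 420 of both sexes. The other 420 are aged 65 or over and are assumed postmenopausal. The documents give no figures on sex or sterilisation. Let *s* be the share of the 420 who are premenopausal women with tubal ligation or occlusion; every value of *s* below is an assumption.

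- Women = 420*s*; tests at most 2 × 420*s* (one per dose).
- *s* = 1%: 4.2 women, at most 8.4 tests.
- *s* = 5%: 21 women, at most 42 tests.
- *s* = 10%: 42 women, at most 84 tests.

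**Step 5. Illustration of the risk.** Assume 1 pregnancy per 100 women per year, and 11 weeks at risk: 8 weeks unrecognised before Day 1 plus the 3 weeks between doses. Table 21 prints a failure rate below 1% per year only for user-dependent methods, so applying it to occlusion or ligation is a further assumption. Expected pregnancies = women × 0.01 × 11/52:

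- 4.2 women: about 0.009.
- 21 women: about 0.04.
- 42 women: about 0.09.

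**Step 6. Timing.** The summary of changes for Protocol Amendment 2 says that out-of-window visits had already been observed, including the interval from Visit 2 to Visit 3. Dosing was therefore well under way, and the number of affected doses still to be given may be 0.

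**The case against.** The strongest reply is that criterion 5 must be read to its last line. That line sends the site to Section 10.5.1, where these women are of childbearing potential and would be tested. The testing rules use the same term that Section 10.5.1.1 defines. Safeguards that do not depend on the label also remain: pregnant women are excluded, a participant who becomes pregnant gets no further dose, and pregnancies are reported at every contact to Month 13. Pregnancy should be rare in this group, and dosing may be complete.

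Most of this stands, and it limits the consequence. The cross-reference makes Section 10.5.1 the likelier governing text. It does not remove the conflict, because the contrary definition is printed in the criterion itself, no precedence is stated, and Section 5.1 tells sites that adherence to the criteria is essential.

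It could also be said that the documents do not show which definition the sponsor intended, so Section 10.5.1.1.1 and Table 21 could be changed instead. That would restore consistency too, but the cross-reference and Table 21 both favour changing criterion 5.

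A reader might infer that any site following criterion 5 skips the test, or that women went untested. The documents do not support either: the criterion also contains the cross-reference, a site may test regardless, and no omitted test is reported.

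A reader might also infer an effect on the primary analysis, because SAP Table 9 removes participants who fail entry criteria from the per-protocol sets. The documents show no such case, and the endpoint definitions, power calculation and alpha do not use childbearing status.

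**Conclusion.** Criterion 5 conflicts with Section 10.5.1.1.1 and Table 21 in the current protocol text. A site relying on the inline definition may omit the urine test before each dose in premenopausal women with tubal ligation or occlusion; a site following the cross-reference would test them. This is an internal inconsistency of minor weight, and correcting it is optional rather than pressing. Endpoints, power and alpha are not affected.

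The number of women is not in the documents. The range of about 4 to 42 rests wholly on assumed shares of 1% to 10%. Under the further assumptions in the working, even the top of that range gives fewer than 0.1 expected pregnancies across the trial. The textual conflict is certain; whether it changed practice at any site is unknown.

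**What to change.** - **Criterion 5.** Delete the inline definition and admit female participants of non-childbearing potential as defined in Section 10.5.1.1.1. This also settles the salpingectomy mismatch.
- **Cross-reference.** Keep Section 10.5.1 for women of childbearing potential, and point to Section 10.5.2 (Table 21) for adequate contraception.
- **Table 21.** Change the entry to bilateral tubal occlusion (including ligation), so that women with a ligation do not appear to need a second method.
- **Conduct.** Test these women before any remaining dose. If no dose remains, this is a wording correction only.

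The cost is a few lines of protocol text, with ethics committee approval where Section 10.1.1 requires it, and at most two urine tests per affected woman, at visits where the same test is already done for others. No SAP text, eCRF field or programming changes.

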5.2. Exclusion criteria for enrollment

Adherence to criteria specified in the protocol is essential. Exclusion criteria deviations are not allowed because they can potentially jeopardize the scientific integrity or regulatory acceptability of the study or safety of the participant.

The following criteria should be checked at the time of study entry. The potential participant MUST NOT be included in the study if ANY exclusion criterion applies:

5.2.1. Medical conditions

1. Current diagnosis or history of autoimmune disorder(s). Refer to [Table 19](#) for conditions that constitute autoimmune disorder(s).
2. History of any reaction or hypersensitivity likely to be exacerbated by any component of the vaccine.
3. Hypersensitivity to latex.
4. Acute or chronic clinically significant pulmonary, cardiovascular, hepatic or renal functional abnormality that appears uncontrolled, as determined by history or physical examination.
5. Any confirmed or suspected immunosuppressive or immunodeficient condition, based on medical history and physical examination (no laboratory testing required).
6. Recurrent history or uncontrolled neurological disorders or seizures.
7. History of Guillain-Barré syndrome.
8. Diagnosed with narcolepsy; or history of narcolepsy in a participant's parent, sibling or child.
9. Diagnosed with cancer, or treatment for cancer within 3 years.
 - Persons with a history of cancer who are disease-free without treatment for 3 years or more are eligible.
 - Persons with a history of histologically-confirmed basal cell carcinoma of the skin successfully treated with local excision only are accepted and are eligible, but other histologic types of skin cancer are exclusionary.
 - Women who are disease-free 3 years or more after treatment for breast cancer and receiving long-term prophylaxis (for example, with tamoxifen) are eligible.
10. Documented human immunodeficiency virus-positive participant.
11. Any clinically significant* hematological laboratory abnormality.

*The investigator should use his/her clinical judgement to decide which abnormalities are clinically significant.

12. Bedridden participants.
13. Any other clinical condition that, in the opinion of the investigator, might pose additional risk to the participant due to participation in the study.

5.2.2. Prior/Concomitant therapy

1. Use of any investigational or non-registered product (drug, vaccine or medical device) other than the study vaccine/product during the period beginning 30 days before the first dose of study vaccine/product (Day -29 to Day 1), or planned use during the study period.
2. Administration of long-acting immune-modifying drugs at any time during the study period (e.g. infliximab).
3. Administration of immunoglobulins and/or any blood products or plasma derivatives during the period starting 3 months before the first dose of study vaccine/product or planned administration during the study period.
4. Chronic administration (defined as more than 14 days in total) of immunosuppressants or other immune-modifying drugs during the period starting 3 months prior to the first vaccine/product dose. For corticosteroids, this will mean prednisone equivalent \geq 20 mg/day. Inhaled and topical steroids are allowed.

5.2.3. Prior/Concurrent clinical study experience

1. Concurrently participating in another clinical study, at any time during the study period, in which the participant has been or will be exposed to an investigational or a non-investigational vaccine/product (drug or medical device).

5.2.4. Other exclusions

1. Pregnant or lactating female.
2. Female planning to become pregnant or planning to discontinue contraceptive precautions within 2 months after completion of the vaccination series.
3. History of or current chronic alcohol consumption and/or drug abuse.
4. Any other clinical condition that, in the opinion of the investigator, might pose additional risk to the participant due to participation in the study.
5. Any study personnel or immediate dependents, family, or household member.

5.3. Lifestyle considerations

Not applicable

5.4. Screen failures

Screen failures are defined as participants who consent to participate in the clinical study but are not subsequently randomly assigned to study intervention.

